1.0 BACKGROUND

Recent analyses have indicated that physical activity reduces mortality risk among patients with renal cell carcinoma (RCC), and gastrointestinal cancer, particularly colon cancer¹. Physical activity also provides additional benefits for patients undergoing treatment for cancer such as improved quality of life and sleep, and reduced treatment-related fatigue². However, individuals receiving treatment for RCC and gastrointestinal cancer often fail to engage in sufficient physical activity. Many cancer survivors experience a decrease in their physical activity after diagnosis² and the majority of RCC and gastrointestinal cancer survivors do not meet the recommended guidelines for physical activity³. Traditional physical activity interventions require significant resources and present substantial barriers for participants (travel, time commitments, etc.). In contrast, mobile technologies enable delivery of interventions with significantly fewer resources. These technologies also facilitate the delivery of just-in-time adaptive interventions (JITAIs) in which intervention support is provided at only at times when an opportunity for positive changes exists.⁴ The purpose of this support the development of a JITAI in RCC and gastrointestinal cancer patients. Evaluation of the acceptability and efficacy of three intervention strategies (affective framing, intention planning, goal-setting, and savoring) will determine their inclusion in the JITAI.

2.0 STUDY OBJECTIVES

Aim 1. Determine the feasibility and acceptability of the proposed mobile technology intervention to increase physical activity patients receiving treatment for renal cell carcinoma and gastrointestinal cancer.

Aim 2. Evaluate the effect of the proposed intervention components (affective framing, intention planning, and goal-setting) on changes in physical activity.

3.0 STUDY DESIGN

3.1 Overview of Study Design

For this project, we will enroll 50 participants diagnosed with renal cell carcinoma or gastrointestinal cancer in an eight-week study. Using a micro-randomized design, participants will receive affective framing messages and intention planning prompts on a randomized schedule, such that participants will receive each message type on 50% of days.

4.0 STUDY POPULATION

4.1 Inclusion Criteria

- 1) Males and females 18 years to 89 years of age
- 2) Diagnosed with renal cell carcinoma or gastrointestinal cancer
- 3) < 150 minutes of weekly moderate-to-vigorous physical activity, as per PAVS survey
- 4) Own a smartphone (required for syncing the Fitbit device).

4.2 Exclusion Criteria

- 1) Medical condition contraindicating exercise participation
- 2) Cognitively unable to give informed consent.
- 3) Unable to read and communicate in English

4.3 Participant Recruitment and Retention

We will recruit participants from the clinics in the UT Southwestern Harold C. Simmons Comprehensive Cancer Center (SCCC).

5.0 STUDY PROCEDURES

5.1 Informed Consent

Individuals will go through the informed consent process prior to completing any study activities. Study personnel will explain the details of the study to the potential participant and then give him or her time to read through the informed consent document. Study personnel will then go through the document with the potential participant and answer any questions he or she may have

5.2 Screening

Potential participants will be screened for eligibility based on all inclusion and exclusion criteria, detailed in sections 5.1 and 5.2. All participants who are screened will complete the Demographics Form.

5.3 Baseline

Study assessments (described in section 6.0) will be collected at initial visit.

5.4 Treatment and Study Intervention

Participants will receive a Fitbit Versa and instructions on its use. Participants will be asked to wear the device for eight weeks, removing it only for charging and when engaging in activities in which the device could be submerged in water beyond its recommended depths (water resistant up to 50 meters).

Manual Connection and Pre-Authorization: At baseline, a research staff member will create a unique email and password combination in order to create an account on Fitbit.com.

During the account creation process the following information will be entered:

- First Name: A de-identified placeholder name will be entered
- Last Name: A de-identified placeholder name will be entered
- Date of Birth: The first day of the month of birth will be entered OR The first day of the year of birth will be entered.
- Gender/Sex: The participant's gender will be entered.
- Height: The participant's height will be entered.
- Weight: The participant's weight will be entered.

It is important to note that the personal demographic details - date of birth, gender, height, and weight - are required for accurate estimation of data captured by the Fitbit Device.

The Fitbit account will be connected to a research device. Once the device is connected to the study-generated and study-controlled Fitbit account it will be manually connected to the Fitabase platform and assigned a unique study ID so that data will be synced and available for viewing and downloading by research staff. All data associated with the Fitbit device will be linked to the chosen unique study ID in the Fitabase platform.

Participants will be given the connected Fitbit device and be provided with the associated email/password so that they may login into the Fitbit.com user account, use the online dashboard, and associated mobile applications. They will be informed that research staff will be able to access, view, and download their data through the Fitabase platform. The participant will be given a copy of the Fitabase Terms of Use and the Privacy Policy for review during the consent process. By consenting to use the Fitbit device as part of this study the participants also signals an acceptance of the Fitabase Terms of Use and Privacy Policy.

At enrollment, participants will indicate a preferred time to receive affective framing messages and EMA prompts (morning), and intention planning prompts (evenings).

Ecological momentary assessment.

Each morning during the eight-week intervention, participants will receive questions about their current affect, intent to engage in physical activity, and self-efficacy for engaging in physical activity. At each request, participants will be given the option to “snooze” the request for up to one hour. The assessment questions will be viewed and responded to on the Fitbit Versa device. We will utilize the Fitbase Engage platform (see Figure 3), which utilizes the Fitbit SDK to deliver assessments and message prompts via the Fitbit Versa. Assessment questions have been validated for their use in EMA.⁵⁻⁷ Daily questions will include:

Figure 3. Representations of messages delivered via the Fitbase Engage platform.

*Actual messages will be customized as described below.

Physical Activity Intention (One item; 1 strongly disagree to 5 strongly agree)

“I intend to meet my goal of XXX steps today”

Physical Activity Self-Efficacy (One item; 1 not confident at all to 5 completely confident)

“I believe I can complete my goal of XXX steps today.”

Affect (Nine items assessing positive and negative affect; 1 not at all to 5 extremely)

“How (happy, cheerful, relaxed, stressed, anxious, angry, depressed, energetic, fatigued/tired) do you feel right now?”

Affective Framing Messages. After completing the daily EMAs, participants may receive an affective framing message. Message delivery will occur on a 1:1 randomization schedule, such that participants will receive messages on 28 of the 56 intervention days. The study biostatistician will generate randomization schedules for each participant using block randomization with variable block sizes. Messages will be randomly selected from a pool of 14 messages, meaning each message will be received twice during the eight-week study. Messages will emphasize potential improvements in mood, energy, and calmness.^{8,9} Examples of these messages:

“Research has shown that physical activity often results in improved mood.”

“Most people report feeling happier and more relaxed after exercise.”

Weekly Goal Setting. Each Sunday evening, participants will receive a prompt to select a step goal for the upcoming week. Along with this prompt, participants will receive feedback on their activity during the previous week. Participants will receive either: 1) the average daily number of steps taken during the previous week, or 2) the highest daily number of steps taken during the previous week.

Intention Planning Prompts. Delivery of these messages will occur on a 1:1 randomization schedule, such that participants will receive messages on 28 of the 56 intervention days. Planning prompts will be delivered in the evening at a time preferred by the participant. At each request, participants will be given the option to “snooze” the request for up to one hour. Using a drop-down

menu, participants will be able to indicate the time, duration, and location to complete the following prompt:

“Tomorrow, at (time), I will walk for (duration) minutes at (location).”

Activity recognition. We will utilize Fitbit SmartTrack feature to automatically detect physical activity bouts. The SmartTrack settings will be customized to identify all physical activity bouts of ≥ 10 minutes. Approximately one hour after completion of a physical activity bout, participants will be asked to report on their current affect and reflect upon their experience during the physical activity bout. Delivery of these assessments will occur after each activity bout; however, in the event of multiple activity bouts occurring in one day, assessments will be limited to the first activity bout of that day. Participants will be given the option to “snooze” for up to one hour if they are unavailable.

Affect (Nine items assessing positive and negative affect; 1 not at all to 5 extremely)

“How (happy, cheerful, relaxed, stressed, anxious, angry, depressed, energetic, fatigued/tired) do you feel right now?”

Remembered Experience (One item; 1 very good to 5 very bad).

“Think back to how you felt during your physical activity today - How do you remember feeling?”

Savoring – After completing the EMAs, participants will receive the savoring messages after 50% of their detected activity bouts (1:1 randomization schedule). Participants will receive imagery-based prompts, as those have been shown to elicit more positive affect responses compared to descriptive prompts (Nelis et al 2015). Delivery of the savoring prompts will occur over approximately 1-minute, with pauses interspersed between prompts to allow for the participant to imagine their experience (see below).

“Thinking back to that physical activity bout, try to create an image of that in your mind. Spend a moment re-living the activity.”

(10 seconds)

“Replay that memory as if you were watching a movie in mind.”

(10 seconds)

“What could you see around you?”

(10 seconds)

“What could you hear?”

(10 seconds)

“How did you feel in that moment?”

(10 seconds)

“What was happening around you?”

(10 seconds)

“What did you do immediately after your activity?”

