A repeated-measures mixed effects model will be used as described in Klasnja et al. (2015) with participant and time as random effects and other effects as fixed. Daily step count will be the dependent variable while main effects of affective framing intervention (message/no message) and linear time effects will be within-subjects factors, and an intervention by time interaction term will be included. We also will consider more complex effects of time (e.g., quadratic effects). We will include scores of the Physical Activity Intention, Physical Activity Self-Efficacy, and Affect as time-varying covariates. As described in Klasnja, et al. (2015) we will include the scores for the day prior to the intervention so the covariates will not be affected by the intervention. We will also classify each day as a cancer treatment day (i.e. day on which chemotherapy or radiation therapy is received) or not and presence/absence of cancer treatment will also be a time-varying covariate. A time lag is not needed for this covariate as the timing of cancer treatment will not be influenced by the intervention. Presence/absence of an implementation planning message on each day will also be included as a time-varying covariate and an affective framing by planning message interaction will be included to assess synergistic effects of the two messages. The baseline measurement of theoretical moderators of physical activity behavior change (Physical Activity Stage of Change, Physical Activity Self-Efficacy, Multidimensional Outcome Expectations for Exercise Scale) and psychosocial characteristics Functional Assessment of Cancer Therapy – General, Quick Inventory of Depressive Symptomatology – Self-Rated, Brief Fatigue Inventory) will be considered as covariates as will other baseline demographic and clinical variables determined to improve the fit of the final model.

Hypothesis 2b: *Participants will have greater daily step counts on days receiving the implementation planning message compared to non-message days.*

The same repeated-measures mixed effects model described for Hypothesis 2a will be used for this hypothesis. Only the interpretation of the results will be different as the presence/absence of the implementation message will be the main effect and the affective framing intervention will be considered the covariate.

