The study design for Aims 2a and 2b will require subjects to be randomized each day to receive the intervention or not. Each day there will be a 50% probability of receiving the intervention (1:1 randomization schedule) so that the average subject will receive the intervention on 28 of the 56 study days. The sample size for Hypotheses 2a and 2b of 50 is based on the sample sizes in the table below which assume 80% power with an alpha=0.05. We also assume that the effect size (standardized difference between treatment groups, similar to Cohen's d) is constant during the 56-day study period. Note that for Cohen's d an effect size of 0.2 or less is considered 'small' (Cohen, 1998) (small effect=0.2, medium effect=0.5, large effect=0.8), therefore, the proposed sample size of 50 will be able to detect effect sizes that are about half of a 'small' effect.

The power analysis for Hypothesis 2c is based on a repeated measures analysis of variance comparison of two groups with 56 repeated observations assuming a correlation between repeated measurements of 0.5, 80% power, and alpha=0.05. Given these assumptions, an effect size of 0.29 can be detected with the proposed sample size of 50. Based on Cohen's guidelines for an ANOVA f-test an effect size of 0.29 is slightly larger than a 'medium' effect (small effect=0.1, medium effect=0.25, large effect=0.4).

Table 1. Sample size calculations.

Hypotheses 2a and 2b		Hypothesis 2c	
Effect Size	Sample Size to Obtain 80% Power	Effect Size	Sample Size to Obtain 80% Power
0.200	17	0.290	50
0.109	50	0.265	60
0.099	60	0.245	70
0.091	70	0.203	100
0.076	100	0.100	402

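### The 2a/2b model names no day-of-week term; prespecifying one would cost almost nothing and could sharpen the message-effect estimates slightly

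*Combined protocol and SAP*

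**What the plan says.** Section 5.4 (Weekly Goal Setting) ties goal selection to a fixed point in the calendar week for every participant: "Each Sunday evening, participants will receive a prompt to select a step goal for the upcoming week". Feedback on the previous week comes with the prompt.

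Section 7.0, Hypothesis 2a, gives the model that also serves 2b. It has random effects for participant and time, a linear time effect, and an intervention-by-time interaction. The day-level covariates are the previous day's intention, self-efficacy and affect scores, whether the day was a cancer treatment day, and the other message type with its interaction. On further time terms it says: "We also will consider more complex effects of time (e.g., quadratic effects". No weekday, weekend or days-since-prompt term is named.

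The power section sets the sample size for 2a and 2b under calculations that "assume 80% power with an alpha=0.05". The effect is a "standardized difference between treatment groups" that "is constant during the 56-day study period". The table pairs 50 participants with an effect of 0.109.

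**The concern.** Walking may vary over the calendar week for two reasons. One is an ordinary weekday/weekend difference. The other is a response to the Sunday-evening prompt that is strongest early in the week and then fades. A linear or quadratic trend over 56 days cannot follow a pattern that repeats every seven days. Whatever part of such a pattern the other covariates do not pick up is left in the residual against which both message effects are tested.

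What is at stake is precision only. The message schedules are randomised by day within participant, so weekday is unrelated to message receipt in expectation. The trial aims at effects of about 0.1 standard deviation, so a small gain from information already held is worth taking.

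**Working it through.** **Inputs from the documents.** N = 50 (section 3.1: "we will enroll 50 participants diagnosed with renal cell carcinoma or gastrointestinal cancer in an eight-week study"). T = 56 days, daily message probability p = 0.5, alpha 0.05, power 80% and d = 0.109 at N = 50 (section 7.0, power calculations and table). The documents give no standard deviation of daily steps and no share of variance due to weekday.

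**Step 1: reproduce the plan's figure.** The micro-randomised-trial formula with a constant effect gives

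noncentrality = N × T × p(1 − p) × d² = 50 × 56 × 0.25 × 0.109² = 700 × 0.011881 = 8.32.

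An F test on 1 and 46 degrees of freedom (50, less three nuisance parameters and one effect) then has power 0.806. The smallest N that reaches 80% is 17, 50, 60, 70 and 100 for effects of 0.200, 0.109, 0.099, 0.091 and 0.076. All five rows of the table match. Without the small-sample correction, the normal approximation gives 47.2 in place of 50. The plan therefore meets its own target without a weekday term.

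**Step 2: effect of adding weekday.** Let R² be the share of within-person daily variance that weekday explains beyond the other covariates. Adding weekday multiplies the standard error by √(1 − R²) and the noncentrality by 1/(1 − R²).

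R² is assumed. For scale, a weekend shift of δ within-person standard deviations gives R² = (2/7)(5/7)δ² = 0.204δ². That is 1.3% for δ = 0.25 and 5.1% for δ = 0.5.

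| Assumed R² | SE falls by | 0.109 × √(1 − R²) | Power at 0.109, N = 50 | N for 80% at 0.109 |
|---|---|---|---|---|
| 0% | 0 | 0.109 | 80.6% | 50 |
| 1% | 0.5% | 0.108 | 81.0% | 49 |
| 3% | 1.5% | 0.107 | 81.8% | 48 |
| 5% | 2.5% | 0.106 | 82.6% | 47 |
| 10% | 5.1% | 0.103 | 84.5% | 45 |

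The third column scales the plan's rounded figure. The effect with exactly 80% power at N = 50 is 0.1082 without the term, 0.1076 at R² = 1% and 0.1054 at 5%.

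**Step 3: simulation.** The setting was 50 people over 56 days, with a random start weekday, a pattern declining through the week, participant means removed, a linear time term and 1,500 runs per setting. Block sizes of 2, 4 and 6 were assumed because the documents give none. The true effect was 0.109.

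- Bias: the mean estimate was 0.108 to 0.110 with or without weekday terms.
- Mean model SE under blocked days, without and with weekday: 0.0378 and 0.0378 at R² = 0; 0.0378 and 0.0373 at 3%; 0.0378 and 0.0359 at 10%.
- At R² = 10% under blocking, the unadjusted model SE (0.0378) was slightly above the empirical SE (0.0372), so leaving weekday out was slightly conservative.

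A separate simulation used a weekday/weekend difference, two independent message schedules, person-level slopes removed and 600 runs per setting. It gave 0.0378 against 0.0376 at R² = 1.3%, and 0.0378 against 0.0369 at 5.1%.

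The R² = 0 result shows the cost: six degrees of freedom out of 50 × 56 = 2,800 person-days do not move the standard error to four decimal places.

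**The case against.** The strongest case against the point is that weekday is one more optional covariate in a pilot. Its benefit rests on an assumed variance share, nothing in the documents is contradicted, and the stated detectable effect holds without it. All of that stands, and it limits the point to a suggestion.

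Some stronger readings are tempting, and the documents do not support them.

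- *A reader might infer that the Sunday prompt builds a seven-day cycle into steps.* A goal chosen for a whole week directly produces shifts in level from one week to the next, which weekday indicators would not remove. A repeating cycle needs the response to fade within the week, or an ordinary weekday/weekend pattern. The documents give evidence of neither.
- *A reader might infer that the model is closed to anything but smooth time terms.* Quadratic time is offered as an example, so other forms remain possible, and the random time effect is not defined.
- *A reader might infer that study-day effects could never absorb a weekday pattern.* That depends on participants starting on different weekdays, which is an assumption because the weekday of Day 1 is not stated. If all started on the same weekday, categorical study-day effects would contain weekday.
- *A reader might infer that a weekday pattern distorts the treatment-day adjustment in a way that matters.* No hypothesis concerns that coefficient. Treatment day and the lagged, goal-worded intention and self-efficacy items may instead absorb part of a weekly pattern, which would reduce the gain from weekday terms.

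What survives is that the plan names no weekday term, that the terms it does name are not designed to capture one, and that leaving the matter to the open wording on time would let the choice depend on the data.

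**Conclusion.** The point holds as a minor, optional gain in precision. There is no bias, no threat to the validity of the 2a/2b tests, and no error in the stated N = 50 at 0.109. If weekday explains 1% to 5% of within-person variance beyond the other covariates, the standard error falls by about 0.5% to 2.5%, power rises by about 0.4 to 2 percentage points, and the saving is about 0.5 to 2.5 participants (50 × R²). At 10% the gain would be about 4 points. The size rests wholly on the assumed share. It also rests on a weekday pattern common to participants and, if study-day effects are fitted, on start weekdays that differ between participants.

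**What to change.** In section 7.0, under Hypothesis 2a, add one sentence that prespecifies day of week as a fixed categorical effect. It would use six indicators derived from the calendar date of each Fitbit daily step count. The effect should enter the shared 2a/2b model and the exploratory moderator models, whatever study-time terms are chosen. Stating the form of the random time effect in the same place would make clear what it can and cannot absorb.

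The cost is that sentence and six degrees of freedom. No new data, participant burden or change to the randomisation is needed. Because weekday cannot be affected by the messages, the adjustment needs no time lag.

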6.1.1 Study Assessments

At baseline and at the end of the eight-week intervention, participants will complete assessments of: 1) potential moderators of physical activity behavior change, and 2) psychosocial outcomes.

Primary outcome measurement:

Fitbit Versa. The primary outcome measure will be daily step counts measured by the Fitbit Versa. Wrist-worn Fitbit devices demonstrate acceptable reliability and validity for measuring step counts.¹³ We will utilize Fitabase, a comprehensive data management platform that utilizes the Fitbit partner-level API, to capture near real-time participant activity data.

Theoretical moderators of physical activity behavior change:

Physical Activity Stages of Change Questionnaire: 4-item scale that assesses current stage of activity.

Physical Activity Self-Efficacy Questionnaire: 3-item scale that assesses self-efficacy for physical activity.

Multidimensional Outcome Expectations for Exercise Scale: 15-item scale that assesses a multitude expectations for physical activity.

Affective associations: 6-item scale that assesses feelings about exercise.

Affective attitudes: 3-item scale that assesses feelings during exercise.

Anticipated affect: 2-item scale that assesses the anticipated affect of regular physical activity.

Psychosocial Outcomes:

Functional Assessment of Cancer Therapy: 19-item scale that assesses quality of life in cancer patients.

Quick Inventory of Depressive Symptomatology – Self-Rated (QIDS-SR): 16-item scale that assesses severity of depression-specific symptoms.

Brief Fatigue Inventory (BFI): 9-item scale that assesses fatigue in cancer patients

Generalized Anxiety Disorder 7 item Scale (GAD-7): 7-item scale that assesses anxiety symptoms.

Pittsburgh Sleep Quality Index (PSQI): 19-item scale that assesses sleep quality and disturbances.

Pain – Frequency, Intensity, and Burden Scale (P-FIBS): 4-item scale that assesses the frequency, intensity, and burden of pain.

Dimensional Anhedonia Rating Scale (DARS): 21-item scale that assesses anhedonia.

Exercise Vital Sign (EVS): 2-item scale that assesses an estimate of an individual's physical activity.

Intervention Acceptability:

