7.0 STATISTICAL ANALYSES

Aim 1. Aim 1 of the proposed pilot study will evaluate the feasibility and acceptability of the proposed intervention. The feasibility of the study will be assessed by the following criteria displayed in Table 1.

Table 1. Feasibility and acceptability measures and benchmarks.

FEASIBILITY		
	Measure	Benchmark
Recruitment	Enrollment rate	7 participants/month
Intervention Adherence	Response rate to intervention messages Response rate to EMA prompts Fitbit use (% of days with > 8 hours wear time)	75% 75% 70%
Retention	Completion of follow-up assessments	90%
ACCEPTABILITY		
	Measure	Benchmark
Intervention satisfaction	Satisfaction questionnaire	75% of participants rate ≥ 4 on 5-point Likert scale

Aim 2.

Hypothesis 2a: *Participants will have greater daily step counts on days receiving an affective framing message compared to non-message days.*

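### Savoring is randomised 1:1 and its efficacy is meant to inform inclusion in the JITAI, but Aim 2 and section 7.0 specify no savoring contrast

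*Combined protocol and SAP*

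**What the plan says.** Section 1.0 sets the decision that the trial is to inform: "Evaluation of the acceptability and efficacy of three intervention strategies (affective framing, intention planning, goal-setting, and savoring) will determine their inclusion in the JITAI". The sentence counts three strategies and names four.

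Section 5.4 allocates savoring at random: "After completing the EMAs, participants will receive the savoring messages after 50% of their detected activity bouts (1:1 randomization schedule"). The EMAs in question are the affect and Remembered Experience items, requested about an hour after a detected bout. If there are several bouts in a day, "assessments will be limited to the first activity bout of that day". Two later measurements matter here. Section 5.4 also states: "Each morning during the eight-week intervention, participants will receive questions about their current affect", and intention and self-efficacy are asked at the same time. Section 6.1.1 states: "The primary outcome measure will be daily step counts measured by the Fitbit Versa".

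Aim 2 in section 2.0 reads: "Evaluate the effect of the proposed intervention components (affective framing, intention planning, and goal-setting) on changes in physical activity". Savoring is not in it. In section 7.0, Hypothesis 2a concerns framing messages, 2b planning messages and 2c the type of step feedback. The exploratory analyses look at EMA moderators of 2a and 2b, and the power section covers 2a to 2c. For the 2a model the plan says: "Presence/absence of an implementation planning message on each day will also be included as a time-varying covariate". Savoring has no term in any model.

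Acceptability is provided for. The Week 10 questionnaire (section 6.1.1) rates specific components of the intervention, and the feasibility table in section 7.0 sets a satisfaction benchmark.

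**The concern.** A component is randomised, the background says its efficacy will count towards a decision, and the analysis section never compares the two randomised conditions. Followed as written, the trial ends with a satisfaction rating for savoring and no estimate of what it does. The inclusion decision would then rest on half of its stated basis, or on a comparison chosen after the data are seen. Several later outcomes could be picked for such a comparison: steps, nine affect items, intention and self-efficacy.

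The draw rule is also open. Section 5.4 speaks of half of all detected bouts, yet the prompt follows an EMA that is given only for the first bout of the day. Any analysis of savoring needs to know when a draw was made and with what probability.

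**Working it through.** **Text check.** Savoring appears in section 1.0 (decision) and section 5.4 (randomisation). It does not appear in Aim 2, Hypotheses 2a to 2c, the exploratory analyses or the power section. Planned savoring contrasts: 0.

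**What could serve as an outcome.** The post-bout EMA precedes the prompt, so its scores are a pre-draw covariate and not an outcome. Next-morning affect and next-day steps follow the draw and are already collected. Bout detection and EMA completion also precede the draw, so limiting a comparison to days with a draw keeps it randomised.

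**The plan's own figure.** Inputs from section 7.0: N = 50, 56 days, randomisation probability 0.5, alpha 0.05, power 80%. For 2a and 2b, take a noncentral F with λ = N × 56 × 0.5 × 0.5 × d² and (1, N − 2) degrees of freedom. At d = 0.109, λ = 700 × 0.011881 = 8.32 and power is 0.807; the smallest N reaching 80% is 50. All five rows of the 2a/2b table reproduce.

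**Scaling.** Detectable d varies roughly as 1/√(number of person-days). Check on the plan's table: 0.109 × √(50/60), √(50/70) and √(50/100) give 0.0995, 0.0921 and 0.0771, against 0.099, 0.091 and 0.076 in the plan.

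**Savoring.** Bout frequency is not given, so I assume 1, 2, 4 or 6 days a week with a bout. I take the feasibility benchmarks as rates: 75% EMA response, and 70% for "Fitbit use (% of days with > 8 hours wear time").

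- Draws per person = 8 weeks × active days × 0.75
- Usable for next-day steps = draws × 0.70
- Usable for next-morning affect = draws × 0.75
- Detectable d = 0.109 × √(56 / usable draws)

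| Active days a week | Draws per person | Usable, steps | d, steps | Usable, affect | d, affect |
|---|---|---|---|---|---|
| 1 | 6 | 4.2 | 0.40 | 4.5 | 0.38 |
| 2 | 12 | 8.4 | 0.28 | 9 | 0.27 |
| 4 | 24 | 16.8 | 0.20 | 18 | 0.19 |
| 6 | 36 | 25.2 | 0.16 | 27 | 0.16 |

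The noncentral F solved directly gives 0.404, 0.286, 0.202 and 0.153 at 4, 8, 16 and 28 usable days. The scaling formula gives 0.408, 0.288, 0.204 and 0.154 there, so the approximation is adequate.

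**Like-for-like comparison.** The plan's 0.109 assumes all 56 days are usable. At 70% wear, 2a and 2b become 0.109 / √0.70 = 0.130.

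**Dose under the two draw rules.** If the draw is made only at a completed first-bout EMA, the share of bouts followed by savoring is 0.5 × completion / bouts per active day. With 1.0, 1.2 or 1.5 bouts per active day (assumed), that is 37.5%, 31% or 25% at 75% completion, and 50%, 42% or 33% at full completion.

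**The case against.** The strongest reply is that the operative plan is consistent with itself. Aim 2 names three components and Hypotheses 2a to 2c match them one for one. The only conflict is with a background sentence whose count disagrees with its own list. On that reading the remedy is a one-sentence correction. This stands as a possible resolution, but the documents do not settle which text is the slip, and section 5.4 still randomises savoring for no stated analytic purpose.

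A second reply is that a null result on next-morning affect or next-day steps would say little about the immediate response to a one-minute imagery prompt. That is correct, and it limits how the estimate may be described.

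Third, the precision figures rest on assumptions. Enrolment requires under 150 minutes of weekly activity, so low bout frequency is plausible. The benchmarks are also treated as independent rates, although someone who has just completed a post-bout EMA is probably more likely than average to wear the watch the next day. The figures are therefore a range. The gap in the plan does not depend on them.

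A reader might infer two stronger things, and the documents support neither:

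- **That asking the EMA before the prompt is a design error.** No document names immediate affect as savoring's outcome, the order keeps Remembered Experience free of the prompt, and it supplies a clean covariate.
- **That the 2a model is wrong to leave savoring out.** Same-day savoring can occur only after a bout, and the morning framing message may itself affect whether a bout happens. Adjusting for savoring would condition on something downstream of the treatment, so leaving it out is defensible.

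**Conclusion.** The concern holds as an omission. Efficacy is part of the stated basis for including savoring, the randomisation that could inform it is in place, and no analysis uses it. The acceptability half of the decision is planned. Hypotheses 2a to 2c are not biased by the omission, and nothing is lost if the contrast is added before the data are examined.

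The contrast would be exploratory. Over 1 to 6 active days a week, at 75% EMA completion and 70% wear, the detectable effect on next-day steps runs from about 0.40 down to 0.16, against about 0.13 for 2a and 2b at the same wear. It reaches Cohen's small effect (0.2) only at about four or more active days a week. It would be a lagged effect and would leave the immediate response to the prompt unmeasured. The change is worth making, but it does not call the trial's specified tests into question.

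**What to change.** 1. **Add one exploratory mixed-model contrast** of savoring versus no savoring, limited to days with a draw at the first-bout EMA. Outcomes: next-day steps and affect at the next morning's EMA. Adjust for the pre-draw post-bout affect score. For next-day steps, also include that evening's planning prompt and the next morning's framing message as scheduled; using the schedule avoids conditioning on later responses. Report the estimate with a 95% CI and label it a lagged effect that does not measure the immediate response.
2. **State the draw rule:** once a day at the first-bout EMA, or at every detected bout. If the first, disclose that savoring will follow fewer than half of all bouts when there are several bouts in a day or EMAs are missed.
3. **If efficacy is not meant to decide savoring's inclusion,** remove savoring from that sentence in section 1.0 instead of adding the contrast.

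The cost of items 1 and 2 is one more exploratory model and a protocol paragraph, with no added items, visits or participants. A draw on day 56 has no next-day outcome within the eight weeks. The once-a-day rule in item 2 carries the lower dose described above. Item 3 changes one sentence.
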